The impact of the SKILLZ Package on our primary outcomes—HIV testing and its care sequelae and contraceptive use—is likely to be moderated by girl's sociodemographic characteristics, such as age, SES status, and her home environment (i.e., siblings, parental HIV status).

5. Literature review

While historically overlooked, the consequences of neglecting to provide adolescents with strong SRH services and potentially causing a painful or damaging transition into adulthood are now well understood. For adolescent girls, pregnancies are much more likely to be high risk. Early pregnancies can also compromise their ability to complete their education, creating a knock-on effect to their future economic earning potential³⁴. They also face an increased risk of exposure to HIV and sexually transmitted infections (STIs) as well as being involved in sexual coercion, and acts of gender-based violence³⁵. Obstacles to receiving access to AFSRH services include inadequate social support, stigma, and detrimental gender and social norms associated with adolescent sexuality including high rates of intergenerational sex and intimate partner violence.³⁶⁻⁴¹ Health care workers often judge, reprimand and may also deny SRH services to adolescents because they believe they are too young to engage in sexual activity.⁴² These issues are magnified for HIV-infected adolescents, where, unlike other chronic diseases among young people, adolescent HIV infection is set apart as a highly stigmatizing disease during a developmentally sensitive time when transitions in self, body and health care are at play.⁴³

The most recent Demographic Health Survey (DHS) showed that while 73.3% of unmarried, sexually active adolescent girls reported not wanting a child in the next two years, only 20.6% were using any contraceptive method to prevent pregnancy and only 40.4% of sexually active adolescent girls aged 15-17 had had an HIV-test in the last 12 months³. The report also indicated that by age 19, more than a third of Zambian adolescent girls report having experienced sexual violence from a male partner and by age 18, a third have been pregnant.³ Furthermore, programmatic data from CIDRZ suggest almost 50% of HIV-infected adolescents that know their status drop out of care within two years of initiating ART.

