GRS has shown that soccer-based interventions combined with strong school and community partnerships and referral networks can change behaviors and make a significant impact on the health of young people.⁵³ In 2009 in South Africa, GRS piloted the SKILLZ-Girl program which addresses the unique needs of young women and adolescent girls. This program was then scaled in South Africa and expanded further into 13 countries in SSA. A recent evaluation of the SKILLZ-Girl program showed that participants significantly improved their knowledge and attitudes surrounding HIV risk for young women, negotiation skills, and sense of self-efficacy. In fact, 68.5% of girls that participated in the SKILLZ-Girl program underwent testing for HIV at the conclusion of the school-based curriculum.⁵⁴ Although SKILLZ-Girl has now served over 26,000 girls in 14 countries, it has never been rigorously evaluated for cost effectiveness and effectiveness.

6. Research questions

Our mixed-methods evaluation aims to assess the effect of the enhanced SKILLZ- girl on HIV testing and SRH related prevention services uptake (Aim 1), the effect of SKILLZ-Plus on HIV retention to care and VLS amongst HIV-infected girls (Aim 2) and identify mediating pathways and moderating factors leading to observed effects (Aim 3). Aim 3 will also assess the cost-effectiveness of the SKILLZ Package.

Our research questions are thus:

- a. What is the impact of enhanced SKILLZ-Girl vs regular SKILL-girl curriculum on HIV testing uptake among adolescent girls (aged 16 and over) over a 24-month period?
- b. What is the impact of enhanced SKILLZ-Club on HIV testing uptake among adolescent girls (aged 16 and over) over a 24-month period?
- c. Among HIV-positive adolescent girls, what is the impact of the SKILLZ-Plus intervention on:
 - a. retention in care and treatment at 6, 12, and 24 months
 - b. viral load suppression at 12 months?

- d. What specific barriers to access to services do the SKILLZ interventions (SKILLZ Girl, enhanced SKILLZ-girl, SKILLZ-Club & Plus) overcome?
- e. What are the mediators of the observed effects?
- f. What are the moderators of the observed effects?
- g. To what degree was the intervention implemented per protocol (fidelity)?
- h. What is the short- and long-term cost-effectiveness of the SKILLZ Package intervention?

7. Research aim(s)/General Objective and Specific Objectives

Aim 1: Assess the impact of SKILLZ over two years on:

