- (i) (a) **HIV testing** and (b) SRH-related prevention services uptake among adolescent girls aged 16-19 in up to 9 intervention schools (with enhanced HIVST, PrEP, and contraceptive method offerings) compared to up to 9 control schools using a quasi-experimental difference-in-difference approach; and
- (ii) **linkage to care and treatment, and viral load suppression and retention at 6, 12, and 24 months** through a cohort model using pre-existing SmartCare data on HIV+ individuals in care to match to adolescent girls aged 16 and over from the same district (Lusaka) who are identified to be HIV+ at any time during SKILLZ Girl or SKILLZ Club participation and enrolled in SKILLZ-Plus.

This will be achieved by i) using a quasi-experimental difference-in-difference approach that compares girls aged 16 and over in 9 SKILLZ control schools compared to 9 schools where enhanced SKILLZ will be delivered with the enhanced HIVST and a variety of contraceptive method offerings; and ii) through a cohort model using pre-existing SmartCare data on HIV+ individuals in care to match to adolescent girls aged 16 and over from the same district (Lusaka) who are identified to be HIV+ at any time during SKILLZ-Girl or SKILLZ-Club participation.

Aim 2: Examine how the intervention works including lessons learned for future implementation by

- (i) conducting a process evaluation to identify mediators, predictors, and barriers to uptake of the SKILLZ-Girl, Club, and Plus curricula both quantitatively through mediation and moderation analyses and qualitatively through a sequential explanatory approach using focus groups discussions, interviews and observation with coaches and girls; and by
- (ii) monitoring fidelity

Aim 3: Estimate the short- and long-term cost-effectiveness and return on investment of the SKILLZ Girl, Club, and Plus curricula for improving health outcomes for adolescent girls.

8. Methodology

a. Study design

We will conduct a mixed-methods evaluation of the SKILLZ intervention using the following approaches:

A **quasi-experimental cohort** of school-aged 16-year old and over females to be followed for a two-year period will be evaluated with a difference-in-difference (DID) approach to estimate HIV testing uptake and sexual/reproductive health services use. Primary and secondary outcomes will be measured at several

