Economic evaluation: We will estimate the short- and long-term cost-effectiveness and return on investment of SKILLZ for improving health outcomes for adolescent girls.

Figure 2. Evaluation enrolment flow

b. Study site and population/Research materials

Lusaka is the capital and the most inhabited city in Zambia. Home to 2 million people, it has the highest HIV prevalence at 14%⁴. The study will take place across all the highly densely populated areas of Lusaka where

[figure not shown]
CIDRZ supports government MoH clinics with ARV services, electronic data management, and youth-friendly trained clinical personnel, and where GRS has been implementing their basic curriculum and events. All schools selected will be secular government schools. Approximately 80% of school-age girls are reported to be in school in Lusaka. To facilitate the evaluation of SKILLZ, all girls enrolled in up to 18 government secondary schools in Urban Lusaka that GRS currently serves will be eligible to participate in the SKILLZ program and will be randomly allocated to either the enhanced or SOC SKILLZ implementation. For measuring impact, only girls aged 16 and over enrolled in Grade 10 at the start of the intervention period will be surveyed and followed because youth aged 16 and over can consent for SRH/HIV services without additional parental permission⁵⁵. (See *Section 9: Ethical Considerations* for details on waiver of parental consent).

c. Selection of participants, sampling methods and sample size

Study Population: In each school, we will recruit all girls in Grade 10 who are at least 16 years old at the start of the intervention period (i.e., the commencement of SKILLZ-Girl). Of the 30,000 youth in Lusaka that have benefitted from GRS services to date, GRS has seen HIV testing uptake of 62% as compared to a baseline of 13% (internal program data). We have powered the sample for our primary endpoints in Aim 1ii to account for attrition anticipated along the cascade (see below). For HIV testing, all eligible girls (estimated to be an average of 100 girls per school) in up to 18 schools is large enough to detect a significant difference in testing uptake if setting statistical significance at $\alpha=0.05$, $\beta=0.2$, ICC=0.1, and an expected testing uptake of 60% (control) and 80% (intervention).

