Cluster randomized controlled trial: We will select up to 18 (2 pilot + 16 for full implementation) schools from the Urban District of Lusaka to receive the SKILLZ-Girl curriculum. Of the total (up to 18), half will be randomly allocated to host the standard SKILLZ-Girl curriculum, and the remaining half (e.g., up to eight) will be randomized to either enhanced SKILLZ-Club. Those schools randomized to standard SKILLZ Girl curriculum will only have access to SOC clubs. Those schools selected for enhanced SKILLZ Girl curriculum will offer SKILLZ Club. See **Figure 3** for study allocation flow.

Figure 3. School Selection Flow Chart

[figure not shown]
ONGOING REFERRAL TO COMMUNITY CARE FOR SERVICES

We anticipate that most of our evaluation cohort will not be HIV-infected. Thus, the retention to SRH analysis drives the sample size calculation of 351 girls using contraception at the end of two years, with, and risk ratio difference of 0.3 (30%) between the SOC and enhanced SKILLZ-Club schools. To realize the 351 needed to meet requirements for estimate sensitivity, we augment the initial sample size receiving the SKILLZ-Girl curriculum accounting conservatively for 25% uptake of SRH methods and multiplying by two to assess the difference within each SKILLZ-Girl model (phase 1) and accounting for attrition across the two years of follow-up (12.5%) resulting in a starting sample size of 3159 $((351/0.25) \times 2) \times 1.025$. **SKILLZ-CLUBS** will act as an extension to the SKILLZ-Girl curriculum enabling participants to seamlessly transition from the SKILLZ-Girl curriculum into the SKILLZ-Club. We anticipate minimal attrition (~15-20%). Participants will spend the majority of the study window in SKILLZ-Club and it is through the SKILLZ-Club affiliation that we will follow-up and ascertain outcomes for those enrolled longitudinally.

For the small minority of girls found to be HIV-infected across all schools where the study will be conducted, we will evaluate linkage to care and on treatment, VLS, and retention in care for a period of two years. These girls will be encouraged to continue on to the HIV positive-specific SKILLZ-Plus facility-based curriculum. We will quantitatively measure the impact of SKILLZ-Plus on linkage to care and treatment, retention and viral load at 6, 12, and 24 months after diagnosis (or since participant is identified by GRS as HIV+) using SmartCare data and compare to an existing matched cohort.

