Difference-in-difference model. The primary outcome is the probability of testing for HIV at any time during the period when SKILLZ is delivered through to 24 months after the final soccer event. The primary analysis for Aim 1 will follow a difference-in-difference (DID) effect between study arms. The outcome of interest will be regressed on an indicator of study arm assignment interacted with a dichotomous variable POST which indicates the outcome after the intervention is implemented; this differentiates baseline and end-line for each study arm, controls for any time dependent variables that might confound the effect, as well as any time-invariant observed or unobserved confounders that might differ between study arm schools. Because of this, the DID is robust to time-invariant unobservable confounders (e.g., school quality) and time trends (e.g., secular increase in testing). Our estimator relies on the assumption of common time trends across intervention and control in absence of the intervention, and of static population. Additionally, we control for baseline individual and school-level moderators that may be unbalanced at baseline after randomization. School-level controls include size, promotion rates, sex composition and repetition and dropout rates (available in the district education office) and individual girls' controls include age, grade, maternal education, HIV knowledge. Clustering by school will be accounted for by a generalized estimating equation approach. We will estimate intention-to-treat (ITT) by including all girls in the evaluation cohort assigned to each arm rather than all girls who actually participated in SKILLZ.

Individual-level matched cohort analysis for HIV-infected: The analysis will follow an individual ITT estimator among individuals found to be HIV-infected, who will then be matched (based on clinic, age, ART state date, and gender) to HIV-infected individuals in the SmartCare database. The outcomes are the proportion of enrolled HIV+ girls who linked to care, who are virally suppressed and retained in care at 6, 12, and 24 months after diagnosis of HIV+ (using national electronic HIV medical record data). We will conduct an ITT analysis for the logistic probability of being suppressed at 6, 12, and 24 months after HIV+ diagnosis, where girl is the unit of analysis. All data will be analyzed using STATA.

Process evaluation: This will involve quantitative and qualitative analyses:

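### The primary outcome is designated differently in sections 4, 8c and 8f, the sample is sized on an outcome that 8f does not mention, and no hierarchy or multiplicity rule is given

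*Combined protocol and SAP*

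**What the plan says.** Four places bear on which outcome decides the study.

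- **Section 8f, difference-in-difference model:** "The primary outcome is the probability of testing for HIV at any time during the period when SKILLZ is delivered", continuing to 24 months after the last event. This is singular, with a window and an analysis method.
- **Section 4, closing paragraph:** it refers in the plural to "our primary outcomes—HIV testing and its care sequelae and contraceptive use".
- **Section 8c, study population:** "We have powered the sample for our primary endpoints in Aim 1ii to account for attrition anticipated along the cascade". Section 7 defines Aim 1(ii) as "linkage to care and treatment, and viral load suppression and retention at 6, 12, and 24 months" among HIV-positive girls. Section 8c then attaches alpha 0.05, beta 0.2, ICC 0.1 and rates of 60% and 80% to HIV testing.
- **Section 8c, later:** "the retention to SRH analysis drives the sample size calculation of 351 girls using contraception at the end of two years".

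Section 8a refers to primary and secondary outcomes without listing them. The matched-cohort analysis in 8f covers girls who link to care and those "who are virally suppressed and retained in care at 6, 12, and 24 months", whereas research question c in section 6 asks about "viral load suppression at 12 months" only. Alpha is stated once, for HIV testing, without saying whether the test is one- or two-sided.

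**The concern.** Readers of different sections would come away with different primary outcomes. On section 8f, a null result for HIV testing is a null primary result. On section 4, a favourable contraceptive result in the same dataset would also be a primary result. On section 8c, so would a favourable result in the HIV-positive subset. With no stated order of testing or division of alpha, the documents do not settle which reading governs.

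The sample-size text adds to this. The outcome that determines enrolment is contraceptive use, yet none of the research questions in section 6 names contraception, and section 8f gives it no definition, time point or analysis. The only outcome with a full set of error rates is HIV testing. The endpoints for which power is claimed have no power calculation.

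**Working it through.** **1. The plan's own figures**

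*HIV testing (8c).* Inputs: 60% vs 80%, alpha 0.05, power 0.80, ICC 0.1, about 100 girls per school, up to 18 schools (9 per arm). I assume a two-sided test, equal clusters and no gain from the difference-in-difference model or covariates.

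- Design effect: 1 + (100 − 1) × 0.1 = 10.9.
- Effective n per arm: 900 / 10.9 = 82.6.
- Power = Φ{[0.2√n − z√(2 × 0.7 × 0.3)] / √(0.24 + 0.16)} = Φ[(1.817 − 1.960 × 0.648) / 0.632] = Φ(0.865) = 0.81.

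This reproduces the stated 0.80. With the 16 full-implementation schools (8 per arm, effective n 73.4), power is Φ[(1.713 − 1.270) / 0.632] = 0.76. A t reference with 16 df gives 0.77 for 9 per arm.

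*Contraception (8c).* 351 / 0.25 × 2 = 2808, and 2808 × 1.125 = 3159, the stated starting sample. The printed multiplier of 1.025 gives 2878, so the formula needs correcting too. The 351 cannot be reproduced, because no base rate is given for the 0.3 difference.

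*Aim 1(ii).* No calculation is given to reproduce.

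**2. Which tests compare the allocated arms**

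| Outcome | Comparison | Tests |
|---|---|---|
| HIV testing | enhanced vs SOC schools | 1 |
| Contraception (one outcome, or uptake and continuation) | enhanced vs SOC schools | 1 or 2 |
| Linkage; suppression × 3; retention × 3 | SKILLZ-Plus vs matched SmartCare cohort | up to 7 |

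The arm-comparison family is therefore 2 or 3 tests.

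**3. Chance of at least one false positive at 5% each**

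If independent, this is 1 − 0.95^k.

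- k = 2: 1 − 0.95² = 9.8%.
- k = 3: 1 − 0.95³ = 14.3%.

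Positive correlation lowers these figures. For three tests with an assumed common correlation of 0.5, simulation gives 12.6%; at 0.9 it gives 8.3%.

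**4. Size of the Aim 1(ii) subset**

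Section 8a expects about 98% of girls who test to be HIV-negative. Applying the remaining 2% to 1,600 girls (16 schools × 100) or to the survey target of 3,200 gives 32 to 64 girls, before any clinic referrals.

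**5. What each remedy does to HIV-testing power (9 schools per arm)**

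- One primary outcome at 0.05: 0.81, unchanged.
- Two co-primaries at 0.025: Φ[(1.817 − 2.241 × 0.648) / 0.632] = 0.72.
- Three at 0.0167: Φ[(1.817 − 2.394 × 0.648) / 0.632] = 0.66.

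**The case against.** The strongest reply is that the analysis plan governs, and it names one primary outcome with a window and a model. Section 8c attaches alpha, beta and ICC to that same outcome. The section 4 sentence is about moderators, not analysis. Sizing a study on its most demanding outcome does not make that outcome primary. The Aim 1(ii) label in 8c may be a slip: section 6 calls the SKILLZ-Plus outcomes Aim 2, section 7 calls them Aim 1(ii), and the calculation to which 8c points concerns contraception. Section 8a also extends the difference-in-difference approach to reproductive health service use generally.

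Much of this stands. Read alone, 8f is clear, and it is the natural text to keep. But 8c is operative sample-size text, not background. It gives primary status and a power claim to one set of outcomes and sizes the study on another. A possible slip still has to be corrected, and a general model statement does not define a contraceptive outcome or its place in the testing order.

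A reader might go further and infer that success could be claimed on any of about nine tests, with a 37% chance of a false positive (1 − 0.95⁹). The documents do not support that. No passage says that a win on any endpoint counts as trial success. The count is a reconstruction (7 to 10 is defensible), and 37% assumes independence among outcomes repeated in the same girls. Up to seven of the nine do not compare the randomized arms at all. Section 4 refers HIV-positive girls in both arms to SKILLZ-Plus, so a favourable result there could not rescue a null enhanced-versus-SOC result.

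**Conclusion.** The contradiction is real and should be resolved before analysis. Sections 4, 8c and 8f do not agree on what is primary. The power claim for Aim 1(ii) has no calculation behind it, and the outcome that sizes the study is missing from 8f. It would be too strong to say that the trial has no deciding result, since 8f names one; the fault is that other sections conflict with it and no rule settles the matter.

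For the enhanced-versus-SOC question, the potential inflation is from 5% to about 10% (two tests) or 14% (three tests). This assumes independence and that each outcome is treated as primary at 5%; it is smaller with positive correlation. The matched-cohort tests are a separate, non-randomized question in roughly 2% of girls and should not be pooled into that figure. The power figures rest on a two-sided normal approximation with 9 equal schools per arm.

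**What to change.** 1. Keep HIV testing, as defined in 8f, as the single primary outcome at the stated alpha of 0.05, and state whether the test is one- or two-sided.
2. Remove the label primary from the other outcomes in sections 4 and 8c. Delete or correct the 8c statement that the sample is powered for Aim 1(ii).
3. Label contraceptive use a key secondary outcome. Define it (uptake or continuation, and when), add its analysis to 8f, and give it a place in the testing order, for example tested only if HIV testing is significant. If the investigators prefer co-primaries, which the dual purpose in section 1c could justify, split alpha and restate HIV-testing power at about 0.72 with 9 schools per arm.
4. Align the 8c sample-size text with that choice, saying plainly that enrolment is sized on a secondary outcome if that remains so, and correct the printed multiplier.
5. Report Aim 1(ii) outcomes as secondary estimates with confidence intervals. Reconcile the suppression time point in section 6 (12 months) with sections 7, 8a, 8c and 8f (6, 12 and 24 months).

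The cost is protocol wording, with no change to enrolment or data collection. The downside of the ordered test is that contraception cannot be claimed confirmatorily if HIV testing is not significant; the downside of co-primaries is the loss of HIV-testing power from 0.81 to 0.72.

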Zambia is struggling to meet the 95-95-95 targets for adolescent women. Despite available public health services, including free HIV testing, prevention, care and treatment, uptake of most health services amongst adolescents in Zambia remains suboptimal, especially for sexual and reproductive health (SRH).^{1,2} HIV testing rates remain low; only 47.5% of girls and 28.5% of boys aged 15-19 years have received an HIV test and learned their results, compared to 86.6% of adult women and 69.1% of men.³ Preliminary results from the 2015-2016 Zambia population-based HIV impact assessment (ZAMPHIA) study show that adolescent girls and young women aged 15-24 years have higher rates of HIV infection compared to their male counterparts and that HIV prevalence among 20-24 year-olds is four times higher among females (8.6%) than males (2.1%).⁴ In addition, whereas over 70% of HIV-infected adults have achieved viral load suppression (VLS), only 34% of adolescent girls have. To further support 95-95-95 targets, contraception is considered the most cost-effective strategy to reduce the burden of mother-to-child HIV transmission among women living with HIV who wish to prevent unintended pregnancy.⁵ The most recent Demographic Health Survey (DHS) showed that while 73.3% of unmarried, sexually active adolescent girls reported not wanting a child in the next two years, only 20.6% were using any contraceptive method to prevent pregnancy.³ Further to this, approximately 7.2% of sexually active adolescents (aged 15-19) reported having had a sexual partner who was 10 or more years older³, placing them at an increased risk of HIV infection and early child-bearing⁶ and the Ministry Of General Education (MOGE) has recorded a five-fold increase in teenage pregnancies among girls in grades 1-12 between 2002 and 2015⁷. The Government of Zambia has recognized that this data clearly points to the need to increase adolescents' awareness and utilization of available health services and ensure innovation in the way these messages are delivered.

b. Overview of research and research gaps (contribution to policy and practice)

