timepoints longitudinally across up to 9 schools offering the enhanced SKILLZ-Girl and SKILLZ-Clubs program and up to 9 schools offering the “standard of care” (SOC) SKILLZ-Girl and SOC Clubs (see Figure 3). Recruitment will take 12 months on a rolling basis. The order in which schools will be selected will be random. Participants will be clustered at the school-level; we will enroll all girls aged 16-years at the commencement of SKILLZ-Girl and in Grade 10 from each participating school.

[figure not shown]
All enrolled girls will be followed over the two-year time period to assess SRH service uptake, including HIV testing. It is estimated that the majority (~98%) of girls testing for HIV will likely be HIV-negative, based on estimates from programmatic GRS data. While HIV-positive girls will continue to participate in the school-based SKILLZ-Girl and Clubs activities and followed for SRH use, they will also be offered contemporaneous enrollment into SKILLZ-Plus upon infection; retention in care and Viral Load Suppression (VLS) at 6, 12, and 24 months will be measured for this subset. See **Figure 2** for details of enrolment flow.

Process evaluation: We will conduct a process evaluation to better understand the casual pathways and effect mediators and moderators using mixed methods approaches, including supplemental qualitative data collection. To investigate reasons why the program components (SKILLZ-Girl, Club & Plus) might fail or succeed in different schools or communities and assess intervention effect mediators and moderators for HIV testing and contraceptive use uptake we will use a mixed methods approach involving: (1) quantitative analyses of baseline survey data for testing how variables can moderate the observed impact of the intervention, and (2) qualitative data collected from a subset of SKILLZ participants in the evaluation cohort and their coaches to further understand potential mediating pathways outlined in Figure 1.

Fidelity monitoring: We will also include measures to monitor fidelity of the intervention implementation, including receptivity to and understanding of the intervention amongst participants, the perceived appropriateness and relevancy of the intervention for adolescent girls in school, and the extent to which the intervention was delivered per protocol in different communities and schools.

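### HIV-testing power is calculated for a two-arm endline comparison, but the primary model is a difference-in-difference whose baseline value is not defined

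*Combined protocol and SAP*

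**What the plan says.** **Outcome and model (section 8f).** The main endpoint is defined as a "probability of testing for HIV at any time during the period when SKILLZ is delivered through to 24 months after the final soccer event". For its analysis the plan says: "The primary analysis for Aim 1 will follow a difference-in-difference (DID) effect between study arms". Arm is interacted with a POST indicator that separates baseline from endline, with GEE by school. The model also controls for baseline factors that "may be unbalanced at baseline after randomization". The listed controls are five at school level (size, promotion, sex composition, repetition, dropout) and four for the girl (age, grade, maternal education, HIV knowledge). Baseline testing is not among them. No link or effect scale is given for this model.

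**Sample size (section 8c).** HIV testing is sized with α 0.05, β 0.2, ICC 0.1, an average of 100 girls per school, up to 18 schools and "an expected testing uptake of 60% (control) and 80% (intervention". No baseline rate and no baseline–endline correlation enters.

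**Baseline testing.** It is probably collected. Section 8a says girls are "followed over the two-year time period to assess SRH service uptake, including HIV testing", the baseline survey in section 8d covers SRH uptake, and the process evaluation in section 8f names prior testing as a moderator. No item or recall window is stated.

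**Allocation and number of schools.** Sections 7 and 8a call the design quasi-experimental, while sections 8b and 8c describe random allocation. Schools number up to 9 per arm in sections 7 and 8a, up to 18 including 2 pilots in section 8c, and up to 16 per arm in section 4. Section 8d targets 3,200 girls.

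**The concern.** A DID estimate is a difference between two changes. Its variance contains the baseline variance and the baseline–endline covariance, and the calculation in section 8c has neither. The outcome, as worded, has no pre-intervention counterpart, so two analysts could fill the baseline term differently and report different primary estimates from the same data.

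If schools are randomised, DID and an endline model adjusted for baseline are both unbiased, and DID is the adjusted model with the baseline slope fixed at 1. In large samples it is therefore never the more precise of the two. What is at stake is precision, and whether the quoted 80% belongs to the analysis that will be run.

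**Working it through.** **1. Reproducing the plan's figure.** For 60% versus 80%, two-sided 0.05 (sidedness assumed), 80% power:

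n per arm = [1.96√(2×0.7×0.3) + 0.8416√(0.24+0.16)]² / 0.2² = 81.2, so 82.

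Design effect = 1 + 99×0.1 = 10.9. Then 82×10.9 = 894 girls, or 8.94 schools, so 9 per arm. Power (pooled–unpooled z): 80.7–82.0% with 9 schools per arm, 75.8–77.3% with 8, 96.6–96.9% with 16. A t reference with 16 df gives 77% with 9 per arm. The stated 80% is therefore an endline comparison with all 18 schools.

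**2. Baseline zero for every girl.** On the risk-difference scale DID = (P_T − 0) − (P_C − 0), which is the endline contrast. Step 1 applies unchanged.

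**3. Baseline means ever or recently tested.** The assumed range ends come from other populations described in the protocol: "HIV testing uptake of 62% as compared to a baseline of 13% (internal program data" (section 8c, no period given) and "only 47.5% of girls and 28.5% of boys aged 15-19 years have received an HIV test and learned their results" (section 1a). A further figure, "only 40.4% of sexually active adolescent girls aged 15-17 had had an HIV-test in the last 12 months" (section 5), lies between them. The school-level correlation r is not given, so it is varied. The individual correlation is assumed to be 0.2.

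- School-mean variance: V(p) = p(1−p)[ICC + (1−ICC)/m]. With m = 100 the bracket is 0.109, so V(0.6) = 0.02616, V(0.8) = 0.01744, V(0.475) = 0.02718 and V(0.13) = 0.01233.
- Covariance: C = √(p0q0p1q1) × [ICC×r + (1−ICC)×0.2/m].
- DID variance: Σ over arms of (V0 + V1 − 2C)/k, with k schools per arm.
- Adjusted variance: Σ over arms of (V1 + b²V0 − 2bC)/k, with common slope b = mean(C)/V0.

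Worked case, k = 9, baseline 47.5%:
- Endline: (0.02616 + 0.01744)/9 = 0.00484, SE 0.0696, power Φ(0.2/0.0696 − 1.96) = 82%.
- DID, r = 0: (0.0436 + 0.05436 − 0.0016)/9 = 0.01071, SE 0.1035, power 49%.
- DID, r = 0.4: (0.0436 + 0.05436 − 0.03715)/9 = 0.00676, SE 0.0822, power 68%.

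Power (%) by formula; the DID range runs from baseline 47.5% to 13%:

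| Schools per arm | Model | r=0 | r=0.4 | r=0.6 | r=0.8 |
|---|---|---|---|---|---|
| 8 | DID | 44–59 | 63–78 | 78–89 | 94–98 |
| 8 | adjusted | 77 | 83 | 91 | 98 |
| 9 | DID | 49–64 | 68–82 | 82–92 | 97–99 |
| 9 | adjusted | 82 | 87.5 | 94 | 99 |
| 16 | DID | 73–87 | 90–97 | 97–99.5 | 99.9–100 |
| 16 | adjusted | 97 | 99 | 99.6 | 100 |

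DID overtakes the plain endline comparison once r exceeds 0.39 (baseline 13%) or 0.59 (47.5%). With 80 girls per school instead of 100, endline power falls by under 1 point and DID power by at most 1.5.

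**4. Small-sample check.** The formulas charge nothing for estimating the slope. Trials were therefore simulated with beta-distributed school rates (ICC 0.1), a normal copula linking baseline and endline, binomial counts and school-level t-tests. With 9 per arm:

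| Observed correlation | Endline | DID | Adjusted |
|---|---|---|---|
| 0 | 76.5–77% | 44–58% | 73.5–74% |
| 0.33–0.36 | 76–77.5% | 61.5–74% | 79% |
| 0.50–0.54 | 76–77% | 75–84% | 84–87% |

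**5. The five school-level controls.** In a balanced linear DID, time-invariant controls entered as main effects leave the arm × POST estimate unchanged. In an endline model they use up scarce school-level information. Five non-prognostic covariates were added (an assumption and a worst case) at copula correlations 0.4–0.8. With 9 per arm, adjusted power fell to about 57–82%, against 61–93% for DID, and was below DID in every cell. At correlation 0 and baseline 47.5% the adjusted model still led (55% versus 45%). With 16 per arm and correlation 0.4 the picture was mixed (adjusted 93–94%, DID 86–95%).

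**The case against.** **HIV testing does not set the sample size.** Section 8c says the SRH retention analysis does. At 3,200 girls in 32 schools, endline power is 97% and DID power is at least 90% from r = 0.4. This stands: restating power changes the quoted figure, not the enrolment target. It does not say which power applies, because 18 schools of 100 give 1,800 girls.

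**The spread rests on assumed inputs.** The documents give no r, no individual correlation and no baseline rate for this cohort, and the lowest DID figures need r = 0. This also stands. A reader might infer that the trial is underpowered; the documents do not support that, since DID power may equally exceed 80%.

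**The adjusted model is not always better.** This stands in part. Near r = 0 it is less powerful than the plain endline comparison, and with all five school controls kept it can lose to DID (step 5). The recommendation must therefore limit those controls.

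**Other stronger readings fail.** DID is not biased under randomisation. The word preassigned in section 4 is compatible with random allocation. Eight versus nine schools per arm follows from the 2 pilots. A logit interaction could not be estimated with an all-zero baseline, but section 8f states no link for this model.

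**Conclusion.** The concern holds as a mismatch between the sizing and the model, together with an undefined baseline term. The stated 80% is that of an endline comparison with 9 schools per arm (81–82% by z-formula, about 77% by school-level t-test). It carries over to the DID only if baseline is zero for every girl and the effect is a risk difference. Otherwise DID power with 9 per arm could lie anywhere from about 49% to 99%, given assumed baseline rates of 13–47.5%, an individual correlation of 0.2 and r from 0 to 0.8.

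Baseline-adjusted endline testing is the better primary analysis on two conditions: schools are truly randomised, and few school-level covariates enter the model. The GEE and the planned girl-level covariates were not modelled. This is an inexpensive improvement, not a proven defect in power.

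**What to change.** 1. Reconcile the quasi-experimental label (sections 7 and 8a) with random allocation (sections 8b, 8c and 8f). State whether the 2 pilot schools are analysed. Reconcile up to 16 schools per arm (section 4) and the 3,200 target (section 8d) with up to 18 schools.
2. State the baseline testing item and its recall window, and confirm that the baseline survey records it. If baseline is meant to be zero for every girl, say so and specify the risk-difference scale.
3. If schools are randomised, make the primary model endline testing regressed on arm, adjusted for baseline testing, on the risk-difference scale, with GEE by school and a small-cluster correction. Drop or strictly limit the five school-level controls. Keep DID as a sensitivity analysis. If allocation is not random, choose between the models on their assumptions.
4. Restate HIV-testing power for the chosen model and the reconciled number of schools, over a range of r.

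**Cost.** SAP wording and a power table, and probably no new data once the survey item is confirmed. Estimating the baseline slope costs about 3–4 points of power against the unadjusted endline comparison when r is near 0 with 8 or 9 schools per arm. There is no gain over DID when r is high and baseline testing is low.
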